#### **6.8      *Reporting of Adverse Drug Reactions to Regulatory Authorities***

The sponsor will submit the ADR to the Regulatory Authorities according to current legislation, and all have to comply with local legislation for safety reporting.

## 6.9 Post-study Safety Collection

If pharmacist or hospital staff becomes aware of an ADR reported by subjects spontaneously after the end of the study, the case will have to be sent to the sponsor, regardless how long after the end of the study.

## 6.10 Special Situations

The following information must be collected and recorded during case processing regardless of the occurrence of AE.

- Medication error (including potential medication error and intercepted medication error)
- Off-label use
- Lack of efficacy
  - The drug was ineffective, did not work, or similar wording, or that the expected effect was not obtained (e.g. subject did not reach the clear yellow liquid poop stage) under the usage and dosage according to the locally approved label.
- Accidental/Occupational exposure
- Misuse/Abuse
- Overdose/Underdose
- Counterfeit/falsified products
- Suspected transmission of an infectious agent *via* a medicinal product
- Drug exposure to foetus *via* mother or father
  - The pregnancy must be reported immediately and within 24 hours from the date of the awareness to the sponsor by completing and sending the “Pregnancy form”. Pregnancy itself is not regarded as an AE, however, any congenital anomaly/birth defect, spontaneous miscarriage, elective termination for medical reasons should be reported and handled as SAE. Pharmacist or hospital staff will continue to provide and record further information about the course and outcome of the pregnancy (spontaneous miscarriage, elective termination, ectopic pregnancy, normal birth, or congenital abnormality) by telephone follow-up.
- AEs in infants following drug exposure from breastfeeding

- Treatment non-compliance
  - In this study, non-compliance of drug administration and liquid intake (see Section 7.3.4) will be recorded as treatment non-compliance.
- Unexpected benefit
  - Cases where the reported term does not reflect a specific reaction, for example “Adverse reaction or Adverse event”
  - Product use issues
  - Product quality issues (only when reported alongside other safety information e.g. an ICSR or other surveillance event (e.g. medication error)).

Details will be described in safety management plan (SMP).

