**METHODOLOGY**

This is a post-marketing multi-site, prospective, non-interventional study. Compound Sodium Picosulfate granules or other similar drugs will be prescribed to the subject based on physicians' clinical judgement.

The study will collect all stipulated events reported from signing the informed consent form (ICF) to about 37(+2) hours after first medication. Contacting the subject remotely by pharmacist or hospital staff will be used to collect adverse events/reactions and other relevant information. No additional tests or examinations will be performed on subjects, no drugs will be provided to the subjects.

- The study staff will register the eligible subjects. The subjects will sign the informed consent, provide contact information. Demographic characteristics (gender, age, nation, height, weight) of subjects will be collected.
- Contact the subjects remotely 37(+2) hours after first medication to collect any adverse events and information on the Compound Sodium Picosulfate granules administration.

All adverse events collected will be sent to the sponsor for case processing.

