### 3 METHODS

#### 3.1 Study Design

This is a multi-site, prospective, non-interventional study. The subject's recruitment should not be influenced by the study protocol and should fall within the current practice.

Subjects who meet the requirements will be followed from signing the informed consent form (ICF) to about 37(+2) hours after first medication to collect AEs, medications and other relevant information with remotely contacted by pharmacist and/or hospital staff. No additional assessments or tests considered as interventional will be required. Any adverse events collected during the subject's interview will be sent to the sponsor for case processing.

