## 5 STUDY PROCEDURES

The study procedure includes following steps:

1. Provide signed and dated written informed consent form prior to any procedure related to the study.
2. Evaluate subjects agreed to participate in study to make sure they meet inclusion and exclusion criteria.
3. Register eligible subjects and collect subject demographics and characteristics (gender, age, nation, height and body weight).
4. Follow up the eligible subjects 37 (+2) hours after the first medication.

For the subject who experienced AE, the following information will be collected to evaluate the safety profile of Compound Sodium Picosulfate Granules in real-world clinical practice.

- Medicinal information (administration time and dosage) and indication
- Concomitant medications
- Medical history
- Relevant lab test and its result: for the subject who experienced AE, collect relevant lab tests and its results subjects may receive as much as possible
- Safety evaluation

All stipulated events reported from signing the ICF to about 37(+2) hours after the first medication. AE information include the nature, the start date and end date, the relationship to the medicinal product, the seriousness, the outcome, and the use of corrective treatment, etc.

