## 6.5 Collection of Adverse Events

The study will collect all stipulated events reported from signing the ICF to about 37(+2) hours after the first medication. Sponsor will capture any adverse events collected during the subject's remotely contact by pharmacist or hospital staff.

Pharmacist or hospital staff will report any adverse events collected during the subject's remotely contact to Ferring (E-mail: PPD ) within the following timelines:

- 1) Fatal events, whether they are related/unrelated, must inform the sponsor immediately (within 24 hours of the knowledge of the event).
- 2) All other AE reports must be sent to the sponsor within 3 calendar days of knowledge of the event or receipt of significant follow-up information.

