## 8 DATA HANDLING

This study collect AEs, medications and other relevant information with remotely contacted by pharmacist and hospital staff. The subjects' data will be input into the database by the delegated staff. The subjects will be identified only by Study ID and subject number in the export database for analysis.

If the written informed consent of a subject is known not to be available in spite of it being required, data for this subject is not entered into or is deleted from the export database.

The safety data (AEs report) filed in AE form will be input into Ferring global safety database. The sponsor is responsible for processing AE/ADR in the safety database.

The coding of AE, medical history, concomitant medication, concomitant non-drug therapies and concomitant surgery terms will be performed. Concomitant medications will be coded using the World Health Organisation Drug Dictionary (WHODRUG) and AEs/medical and surgical history and nondrug therapy terms will be coded using the latest version of MedDRA.

On request, Pharmacist or hospital staff will provide the sponsor with additional data relating to the study, duly anonymised and protected in accordance with applicable requirements.

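### Section 6.10 requires special situations to be recorded with or without an AE, but apart from pregnancy the protocol gives sites no explicit question, route or timeline for those without one

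*Combined protocol and SAP*

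**What the plan says.** Section 6.10 sets a mandatory rule that does not depend on AEs: the listed information "must be collected and recorded during case processing regardless of the occurrence of AE". The list covers medication error, off-label use, lack of efficacy, misuse, overdose or underdose, exposure cases, treatment non-compliance and others. Pregnancy has its own form and a 24-hour limit. Further details are left to the SMP.

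The collection text is not uniform:

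- Section 5 opens its list of detailed items with "For the subject who experienced AE, the following information will be collected". Administration time, dosage and indication are on that list.
- The synopsis, under Methodology, describes the contact more widely: "Contact the subjects remotely 37(+2) hours after first medication to collect any adverse events and information on the Compound Sodium Picosulfate granules administration".
- Section 3.1 follows subjects "to collect AEs, medications and other relevant information with remotely contacted by pharmacist and/or hospital staff", and Section 8 has nearly the same wording.

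The reporting text names AEs. Section 6.5 says "Pharmacist or hospital staff will report any adverse events collected during the subject's remotely contact to Ferring", with 24 hours for fatal events and 3 calendar days for other AE reports. The synopsis says "All adverse events collected will be sent to the sponsor for case processing", and Section 3.1 has an equivalent sentence. In Section 8 the global safety database is filled from the AE form, while subjects' data in general are entered into a study database.

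**The concern.** Section 6.10 places the recording in case processing, which Section 6.7 assigns to the sponsor. The sponsor can process only what it receives. If a site follows Sections 5 and 6.5 to the letter, a subject who took the wrong amount, used the product off label or had no bowel-cleansing effect, and had no AE, need not be asked about it, and the site has no stated duty to send it on.

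Two things are at stake. Special situations without an AE may be missing from the safety record, although Section 1.3 says the study will assess utilisation as well as safety. And those that are recorded would tend to be the ones accompanied by an AE, which gives a distorted picture of how such situations turn out.

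**Working it through.** The documents state no figure for this point, so there is none to reproduce. The check sets the sections side by side.

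1. **Is the 6.10 duty really independent of AEs?** Yes. The opening sentence says so, and the list attaches a condition where one is meant: product quality issues count only when they come with other safety information. The other items carry no such limit.

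2. **Does the contact gather what is needed?** Overdose, underdose and off-label use cannot be recognised without dose, timing and indication. Lack of efficacy is defined in 6.10 as failure of the expected effect under labelled use, so it also needs dosage. Section 5 ties these items to subjects with an AE. The synopsis collects administration information from all contacted subjects. The two conflict. Even on the wider reading, no text names a question on indication for subjects without an AE, on errors, or on whether the expected effect was obtained.

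3. **Is there a route to the sponsor?** The synopsis, Section 3.1 and Section 6.5 each tell sites to send AEs. Both clocks in 6.5 apply to fatal events and other AE reports. Section 8 feeds the safety database from the AE form. It does not link the study database to case processing. Pregnancy is the only listed item with its own form and limit.

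4. **Is 6.10 aligned with the rest of the protocol?** Not fully. For non-compliance it points to Section 7.3.4, but the current text goes from 7.3.3 to 7.4.

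5. **Can the loss be sized?** Let S be a special situation other than pregnancy and A an AE in the same subject. If capture required an AE, the share captured would be at most P(A | S) and the share lost at least 1 − P(A | S). The documents do not give P(A | S). If S and A were independent (an assumption), P(A | S) = P(A), and:
   - at the treatment-emergent AE incidence quoted in Section 1.2.2 for the sponsor's trials, 73% (age 65 or over) and 71% (under 65), the loss is 1 − 0.73 = 0.27 and 1 − 0.71 = 0.29;
   - at an assumed 5% to 30% of subjects reporting an AE, the loss is 1 − 0.05 = 0.95 down to 1 − 0.30 = 0.70.

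   The result runs from 27% to 95% on the choice of AE rate alone. A positive association between S and A would lower it, as would any capture in subjects without an AE. This shows sensitivity to assumptions; it is not an estimate.

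6. **What follows without any rate?** If capture required an AE, every recorded case would come with one, whatever the true association.

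**The case against.** The strongest case on the other side is that the contact is not confined to AEs. The synopsis asks about administration with no AE condition. Section 8 says "This study collect AEs, medications and other relevant information with remotely contacted by pharmacist and hospital staff". The appendix synopsis has AEs and relevant information reported after the procedure. Section 6.5 refers to stipulated events, a term not defined as AEs only. Section 8 enters subjects' data into a study database. Nothing forbids a site from sending a special situation without an AE, and the SMP may hold the form and timeline.

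Much of this stands. A reader might infer that sites ask about AEs only; the synopsis, Section 3.1 and Section 8 contradict that. A reader might also infer that the 6.10 rule cannot be met. The documents do not support that either: the instructions are incomplete, but they do not make compliance impossible, and the SMP has not been seen.

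What the objection does not remove is the conflict between Section 5 and both the synopsis and Section 6.10, or the absence of an explicit site duty. The wider wording names no question on errors or effect and creates no obligation to send such a case. The stipulated events are undefined, and 6.5 goes on in AE terms.

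It is also fair that Section 7.3.3 plans no frequency for medication error, off-label use or lack of efficacy. No planned estimate of those frequencies is therefore biased by this gap.

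**Conclusion.** The point holds as a gap and an internal conflict. Section 6.10 makes recording mandatory whether or not there is an AE; Section 5 ties the key facts to an AE; the synopsis does not; and apart from pregnancy no explicit question, route or timeline exists for a special situation without an AE. Capture is not assured and would tend to follow the presence of an AE.

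The size is unknown. It is tempting to conclude that most such cases would never reach the sponsor, but that needs a low assumed AE rate, independence, and no capture at all in subjects without an AE. The documents give none of these, and at the only AE incidence used from them (71% to 73%) the same reasoning gives 27% to 29%. It is equally tempting to infer that special situations would inflate AE incidence. The documents do not settle this: Section 6.7.6 does not list them among events not recorded as AEs, and no text says they will be counted as AEs. If only cases with an AE were captured, the proportion of subjects with any AE could not rise.

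The conclusion rests on the protocol text alone. If the SMP already contains the questions, route and timeline, what remains is to reconcile the sections and refer to the SMP explicitly.

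**What to change.** - **Section 5:** reconcile it with the synopsis and Section 6.10. At the existing 37(+2) hour contact, ask every subject the amount and time taken, the indication, whether any error occurred, and whether the expected effect was obtained.
- **Section 6.5, synopsis and Section 8:** require sites to send every 6.10 special situation to the sponsor with or without an AE, and show how it enters the safety database. State a timeline in the protocol or refer explicitly to the SMP. The pregnancy route stays as written.
- **Section 6.10:** correct the reference to Section 7.3.4.
- **Section 7.3.3:** if these cases are reported, list them separately from AE incidence, over the Safety population.

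The cost is protocol wording, a few more questions per contact and some extra case entries without an AE. The contact is already planned, so no visit is added.

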## 2 STUDY OBJECTIVES

The objectives of this drug intensive monitoring study are to monitor and assess the safety profile of Compound Sodium Picosulfate Granules in the real world clinical practice in Chinese population, including:

- Incidence of known ADRs
- Observe occurrence of unexpected AEs/ADRs
- Incidence and risk factors of SAEs/SADRs

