#### 7.3.3 *Safety Evaluation*

AEs will be coded using the latest version of MedDRA and presented as “Preferred Terms (PT)

and System Organ Classification (SOC)".

Descriptive summary statistics of SAEs, AESIs and other nonserious AEs, related or unrelated to Compound Sodium Picosulfate Granules, will be presented. The main contents include the incidence, seriousness, of known ADRs/AEs and unexpected ADRs/AEs, as well as the occurrence of ADRs/AEs in specific populations. The covariates like age, gender and relevant risk factors (e.g. decreased renal function, non-compliance of drug administration or liquid intake, etc.) for the AE will be examined. Analyses and summary tables will be based upon the registry population.

Statistical analyses will present the overall results as well as separately for the specific populations.

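### Non-compliance with drug or liquid intake is kept as an AE risk factor but has no definition, and the sections conflict on whether it is collected from subjects without an AE

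*Combined protocol and SAP*

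**What the plan says.** - **Analysis.** Section 7.3.3 states that "relevant risk factors (e.g. decreased renal function, non-compliance of drug administration or liquid intake, etc.) for the AE will be examined". Section 2 includes among the study's aims "Incidence and risk factors of SAEs/SADRs".
- **Definition.** Section 6.10 lists treatment non-compliance among its special situations: "In this study, non-compliance of drug administration and liquid intake (see Section 7.3.4) will be recorded as treatment non-compliance". Both the contents list and the body go from 7.3.3 straight to 7.4.
- **Collection in Section 5.** Every registered subject gives demographics. The next list opens with "For the subject who experienced AE, the following information will be collected" and covers administration time and dosage, indication, concomitant medication, history and laboratory results. Liquid intake appears in neither list.
- **Collection elsewhere.** The synopsis (Methodology) has the 37(+2) h contact gather AEs and information on taking the product, with no restriction to subjects with an AE. Section 3.1 similarly mentions medications. Section 6.10 requires special situations to be recorded whether or not an AE occurred, but places this within case processing.
- **Reporting.** Section 6.5 says "Sponsor will capture any adverse events collected during the subject's remotely contact by pharmacist or hospital staff" and sets reporting timelines for AEs only.
- **Missing data.** The only rule is in Section 7.3.1, for demographics and baseline: values are not replaced, and missingness is displayed.

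**The concern.** A risk-factor comparison needs the factor measured in the same way in subjects with and without the event. Here the factor has no written criterion, one of its two components (liquid intake) has no data item, and the section that sets out procedures ties the other component to having had an AE. The safety population (Section 7.2) includes anyone who took at least part of the drug. Partial takers without an AE are therefore in the denominator, yet Section 5 has no item that would identify them.

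At stake is the risk-factor part of the objective. The report could have nothing to compare, could show a link with poor compliance created by the recording, or could pool judgements made by each site's own standard. Having no formal tests (Section 7.3) removes p-values but not this kind of bias.

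**Working it through.** The plan gives no sample size, event rate or association for this point, so there is no figure to reproduce. The check has two parts.

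**1. What the text provides**

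| Element needed | Subjects with an AE | Subjects without an AE |
|---|---|---|
| Definition of non-compliance | none (6.10 points to a missing section) | none |
| Liquid-intake item | none listed | none listed |
| Administration time and dosage | listed in Section 5 | not in Section 5; implied by the synopsis and 6.10 |
| Reporting route | Section 6.5 | none stated for non-compliance |
| Rule for unrecorded compliance | none | none |

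**2. What unequal recording would do when compliance has no true effect**

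Inputs, all assumed:
- AE risk p = 5% to 70%. The documents give no rate for this study. Section 1.2.2 reports 71–73% treatment-emergent AEs in earlier trials, so 70% serves as the upper end.
- True non-compliance q = 5% to 20%.
- Probability that non-compliance is recorded: s1 = 1 with an AE, s0 = 0 to 1 without.
- Unrecorded subjects are counted as compliant.

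Formulas:
- OR = [q·s1/(1 − q·s1)] / [q·s0/(1 − q·s0)]. This does not depend on p.
- RR = {p·q·s1/[p·q·s1 + (1 − p)·q·s0]} / {p(1 − q·s1)/[p(1 − q·s1) + (1 − p)(1 − q·s0)]}.

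Example with 1,000 subjects, p = 10%, q = 20%. There are 100 AE subjects (20 non-compliant) and 900 AE-free subjects (180 non-compliant).
- s0 = 0: (20/20)/(80/980) = 1.000/0.0816 = 12.25.
- s0 = 0.25, so 45 of the 180 are recorded: RR = (20/65)/(80/935) = 0.308/0.0856 = 3.60. OR = (0.20/0.80)/(0.05/0.95) = 4.75.
- s0 = 1: (20/200)/(80/800) = 1.00.

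Ranges over q = 5% to 20%, with s1 = 1:

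| s0 | OR | RR, p = 5% | RR, p = 10% | RR, p = 30% | RR, p = 70% |
|---|---|---|---|---|---|
| 0 | infinite | 21.00–24.75 | 10.47–12.25 | 3.46–3.92 | 1.45–1.54 |
| 0.25 | 4.16–4.75 | 3.61–4.10 | 3.19–3.60 | 2.16–2.38 | 1.31–1.36 |
| 0.50 | 2.05–2.25 | 1.95–2.13 | 1.86–2.02 | 1.57–1.67 | 1.19–1.22 |
| 1 | 1.00 | 1.00 | 1.00 | 1.00 | 1.00 |

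If unrecorded subjects are instead left missing and only AE subjects have data, the AE-free column of the two-by-two table is empty and no association with AEs can be estimated.

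**The case against.** A reader might infer that non-compliance can reach the sponsor only through AE cases, and that the analysis is therefore bound to show a strong false association. The documents do not support either step.

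- Section 6.10 requires recording with or without an AE, and the synopsis has the contact collect administration information from subjects generally. Section 8 describes a study database beside the safety database, and Section 6.10 gives pregnancy, which is not an AE, its own reporting route. Section 6.5 is thus not shown to be the only channel.
- The inflated ratios need unrecorded subjects to be counted as compliant. No section says so, and the baseline rule in 7.3.1 leans the other way.
- The size is not fixed. At 70% AE risk, even zero recording in AE-free subjects gives a risk ratio of only about 1.5.
- Section 7.3.3 promises a descriptive examination, not a risk ratio. The Section 2 objective concerns serious events, whereas the illustration uses any AE and does not carry over directly.
- Section 6.10 leaves detail to a safety management plan, which is not among the documents and may contain forms and a working definition.

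These points stand against the strong reading. They do not supply the missing section, a liquid-intake item, or agreement between Section 5 and the synopsis. The synopsis and Section 3.1 do not mention fluids. The Version History explains how the gap may have arisen; the defect lies in the current text.

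**Conclusion.** The point holds as an inconsistency with consequences for the analysis. The covariate in Section 7.3.3 has no definition in the protocol and no listed liquid-intake item, and the sections conflict on whether drug-intake data exist for AE-free subjects. If Sections 5 and 6.5 are followed as written, the comparison either cannot be made (unrecorded values left missing) or is open to a spurious association (unrecorded counted as compliant).

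In that second case, under no true effect and the assumptions above, the odds ratio is about 4.2–4.8 with 25% recording in AE-free subjects and 2.05–2.25 with 50%. With none recorded, the risk ratio is about 10.5–12.3 at 10% AE risk but about 1.5 at 70%. If the synopsis and Section 6.10 are applied equally to everyone, this source of bias is absent and the ratio is 1.0. The figures show how sensitive the result is to the recording; they do not forecast what the study will find. The gap in definition remains in every case.

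**What to change.** 1. Reconcile the synopsis, Section 5 and Section 6.10 so that the same fixed questions on sachets taken, their timing and liquid intake are put to every subject at the existing 37(+2) h contact.
2. In 6.10, replace the reference to 7.3.4 with a written definition of non-compliance, judged against the local prescribing information that Section 3.2 already invokes.
3. In 6.5, give special situations without an AE a reporting route.
4. In 7.3.3, state that unrecorded compliance is treated as missing, not as compliant, and show the number missing separately for subjects with and without an AE.

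If the sponsor does not want these items, delete non-compliance from the 7.3.3 covariates and report it only as a description of AE cases.

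The cost of the full fix is a slightly longer call and a protocol amendment, handled under Section 10.1. Deleting the covariate adds no data collection but still needs the amendment, and it gives up this part of the risk-factor question.
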